### 3.7.2.4 Cervical Mucus

Details on cervical mucus score calculations are in Section 5.3. The following information will be summarized for all subjects in the Safety population using descriptive statistics.

- Was cervical mucus too thick to be collected?
- Was cervical mucus collected prior to TVUS?
- Viscosity score
- Ferning score
- Spinnbarkeit score
- Cellularity score
- Total cervical mucus score

A plot of the total cervical mucus score by visit will be done for the Safety population.

### 3.7.2.5 Transvaginal Ultrasound and Hormones

Transvaginal ultrasound (TVUS) examinations will be summarized at all assessed visits for the Safety population. The following endpoints will be summarized for the screening visit, each of the 3 treatment periods, delayed pill period and missed pill period:

- Was postovulatory image seen?
- Right Ovary
  - Presence of follicles
- Left Ovary
  - Presence of follicles
- Any abnormalities found?

For each of the 3 treatment periods subjects will be counted as having the outcome (e.g, had a postovulatory image seen) if the outcome happens at least once during the treatment period. Summaries will also be done by infringement type.

TVUS largest follicle diameter measurement: The time course of the diameter will be presented graphically along with P4 and E2 (see below) at each visit.

#### Hormones

Profile graphs for each subject will be prepared for P4 and E2 and will include largest follicle diameter (largest diameter for each day) also.

### 3.8 Pharmacokinetics

The PK profile of LNG after administration of norgestrel 75 mcg will be assessed at different times during the study.

The PK profile of LNG will first be assessed at Day 1 after the first administration of norgestrel 75 mcg in fasted conditions.

All the subjects will be sampled at different time points after administration as presented in the table below:

#### PK Sampling Schedule at Day 1

	Sampling times							
	predose	1h	2h	4h	6h	8h	12h	24h
Odd #		X		X		X		X
Even #	X		X		X		X	

During the first visit of the 3rd week of treatment, all the subjects will be sampled at different times points. If the visit is in the morning, they will be sampled predose and between 0.5h and 2h post administration. If the visit is in the afternoon, they will be sampled between 5h and 9h post administration. The plasma concentration(s) for each subject will be reported with the nominal time of sampling.

During the DMP period, the sampling schedule will depend on the arm the subjects had been randomized in (see table below).

#### PK Sampling Schedule during the DMP Period

	DMP 2						DMP 3					
	V2 R-1	V2 R			V2 R+1		V3 R-1	V3 R			V3 R+1	
	T2 R-1 + 8h	T2 R-1 + 3h	T2 R-1 + 5.5h	T2 R-1 + 6h	T2 R-1 + 7.5h	T2 R-1 - 0.5h	T3 R-1 + 8h	T3 R-1 + 3h	T3 R-1 + 5.5h	T3 R-1 + 6h	T3 R-1 + 7.5h	T3 R-1 - 0.5h
Arm A	X	X	X		X	X	X			X		X
Arm B	X			X		X	X	X	X		X	X

The mean plasma concentration for each time point will be calculated:

- V2/3R-1: C2/3R-1,8h (Arm A + Arm B)
- V2/3R: C2R-1,27h (Arm A), C3R-1,27h (Arm B), C2R-1,29.5h (Arm A), C3R-1,29.5h (Arm B), C2R-1,30h (Arm B), C3R-1,30h (Arm A), C2R,1.5h (Arm A), C3R,1.5h (Arm B)
- V2/3R+1: C2/3R+1,-0.5h (Arm A + Arm B)

The concentration of LNG will also be determined in all subjects during the 1st visit of study week 5 (V21) and 9 (V31). The sample will be drawn within 30 minutes of the mucus analysis. The concentrations will be reported as C21 and C31.

LNG concentrations at each timepoint will be summarized in a table presenting summary statistics (sample size, mean, median, SD, minimum, and maximum) for all treatment periods for the PP population. A figure will be created to display the mean concentrations at each timepoint for all treatment periods.

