### 2.2 Objectives

The primary objectives of the study are:

- to determine the effect of a delayed intake of 6 hours or of a missed pill on cervical mucus score compared to cervical mucus score during reported perfect daily use of norgestrel 75 mcg
- to estimate the duration of the protective effect of cervical mucus after last pill intake of norgestrel 75 mcg during reported perfect use (The protective effect of cervical mucus is considered as present when the score is below or equal 4.)

---

 defined as the day before the delayed intake or the missed pill

The secondary objectives of the study are:

[figure not shown]
- to evaluate and compare the percentage of subjects with a protective cervical mucus score during reported perfect daily use of norgestrel 75 mcg, during a treatment period with a delayed intake of 6 hours and during a treatment period with a missed pill of norgestrel 75 mcg.
- to evaluate and compare the ovarian activity during reported perfect daily use, during a treatment period with a delayed intake of 6 hours and during a treatment period with a missed pill of norgestrel 75 mcg.
- to assess if a combination of cervical mucus score and ovarian status can be considered as a measure of protection from conception during reported perfect daily use, during a treatment period with a delayed intake of 6 hours and during a treatment period with a missed pill of norgestrel 75 mcg.
- to determine levonorgestrel pharmacokinetics after a single dose of norgestrel 75 mcg, at steady state, after a delayed intake and after a missed pill.
- to assess the safety of norgestrel 75 mcg taken daily for 12 weeks.

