### 2.3 Design

This is an exploratory, prospective, multi-center, randomized, cross-over study to assess the effect of norgestrel 75 mcg on cervical mucus and ovarian activity during reported perfect daily use and after a delayed intake of 6 hours and after a missed pill.

Women of reproductive age (18-35 years old inclusive) who meet eligibility requirements will be recruited for this study. This study has a screening period of up to 1 month to demonstrate ovulatory status prior to enrollment followed by three 28-day treatment periods (approximately 3 months) and a possible follow-up of 12 days if ovarian activity shows a follicle  $\geq 15$  mm is observed at the end of period 3 and an end of study (EOS) visit within 5 days. During the treatment period 2 the subjects will be randomized into two arms: Arm A will have a delayed pill intake of 6 hours on D42 ( $\pm 3$  days) and Arm B will have a missed pill (24-hour delayed pill intake on D42 ( $\pm 3$  days)). In the next treatment period, these subjects will cross-over meaning Arm A will have a missed pill (24-hour delayed pill intake) on D70 ( $\pm 3$  days) and Arm B will have a delayed pill intake of 6 hours on D70 ( $\pm 3$  days) (see Figure 1 below).

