		Visits twice a week if follicle < 15 mm  Visits every other day for a maximum of 6 days if a growing follicle ≥ 15 mm identified upon TVUS(b)	Visits twice a week if follicle < 15 mm  Visits every other day for a maximum of 6 days if a growing follicle ≥ 15 mm identified upon TVUS(b)	Delayed/missed pill period Three consecutive days		Visits twice a week if follicle < 15 mm  Visits every other day for a maximum of 6 days if a growing follicle ≥ 15 mm identified upon TVUS(b)		Delayed/missed pill period Three consecutive days			Visits every other day for a maximum of 12 days if a growing follicle ≥ 15 mm identified upon TVUS(c)			
				V2 0+1	V2 0A	V2 0B	V2 0+1		V3 0+1	V3 0A	V3 0B	V3 0+1		
Study medication intake		X	X	X(i)	X(j)		X(k)	X	X(i)		X(j)	X(k)		
Diary completion		X	X	X	X	X	X	X	X	X	X	X	X	X
TVUS	X	X	X	X	X	X	X	X	X	X	X	X	X	X(l)
Mucus analysis		X(m)	X	X(n)	X(o)	X(p)	X(q)	X	X(n)	X(p)	X(o)	X(q)	X	
PK samples		X(r)(s)	X(t)	X(u)	X(v)	X(w)	X(x)	X(t)	X(u)	X(w)	X(v)	X(x)	X	
P4	X	X	X	X	X	X	X	X	X	X	X	X	X	X
E2, FSH, LH		X	X	X			X	X	X			X	X	X(y)
Prior and concomitant treatments	X	X	X	X	X	X	X	X	X	X	X	X	X	X
Adverse events and bleeding patterns	X	X	X	X	X	X	X	X	X	X	X	X	X	X

- (a) Only if follicle ≥ 15 mm is observed after Day 73 AND the criteria for stopping the extra-visits were not fulfilled by Day 84
- (b) Extra visits will be stopped before 6 days if there is no postovulatory image after 6 days
- (c) Extra visits will be stopped before 12 days if there is no postovulatory image after 6 days or if the P4 levels are > 30 nmol/L at 1 visit or > 10 nmol/L at 2 consecutive visits.
- (d) Randomization at 1st visit of treatment period 2
- (e) Vital signs include heart rate, systolic and diastolic blood pressure after at least 2-minute rest and height and weight (at screening only).
- (f) Pap smear to be performed according to current US guideline if an abnormal cervical lesion is detected during the gynecological examination
- (g) At V11 only, before first pill intake
- (h) At V11, last visit of treatment period 1 and last visit of treatment period 2
- (i) Study pill intake will be at 9 am ± 1 hour and will be noted as T2/3R-1 (actual treatment time at Day 41 or Day 69)
- (j) Study pill intake at T2/3R-1+ 6h ± 15 min
- (k) Study pill intake at T2/3R-1 ± 30 min
- (l) TVUS up to observation of postovulatory image

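### The Day R+1 levonorgestrel mean pools both arms, so it averages samples 17.5 h after a delayed pill with samples 47.5 h after the last pill before a missed one

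*SAP*

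**What the plan says.** SAP section 2.2 sets a secondary objective to determine levonorgestrel PK after a single dose, "at steady state, after a delayed intake and after a missed pill".

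Under section 2.3, in period 2 "Arm A will have a delayed pill intake of 6 hours on D42" and "Arm B will have a missed pill (24-hour delayed pill intake on D42". The arms then swap: "Arm A will have a missed pill (24-hour delayed pill intake) on D70", and Arm B has the delayed pill. Footnote (j) of the schedule in section 5.1 times the delayed pill on the day of infringement: "Study pill intake at T2/3 R-1 + 6h ± 15 min".

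Section 3.8, under the PK sampling table for the delayed/missed pill period, states: "The mean plasma concentration for each time point will be calculated". A list of those means follows:

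- **R-1:** one entry for both arms, 8 h after the regular pill.
- **Day R:** entries tied to a period and an arm, for example "C2 R-1,27h (Arm A), C3 R-1,27h (Arm B".
- **R+1:** one entry for both arms, "C2/3 R+1,-0.5h (Arm A + Arm B".

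The section ends with a summary table by time point for all treatment periods in the per-protocol population, and a matching figure. It does not say that either is split by type of infringement.

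**The concern.** Pooling the arms at R-1 is sound, because every woman is then 8 h past a regularly timed pill. At R+1 it is not. One arm took a pill the previous afternoon, and the other took none that day. The crossover does not cure this, because it only exchanges the arms. Each calendar period still contains both conditions, so the entry mixes them whether it is read as one mean per period or one mean over both.

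R+1 also carries most of the PK information about a missed pill. By the sampling table, a missed-pill woman has two samples after R-1: one at 30 h and one at R+1. At 30 h she has the same dosing history as a delayed-pill woman just before the delayed pill, whose 29.5 h sample is nearly equivalent. Only R+1 shows what happens when the pill is omitted rather than taken 6 h late.

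The SAP recognises this for the mucus endpoint. Section 3.7.1 restricts the comparison of R-1 with R+1 to the missed pill and labels it as 48 h after treatment. Section 2.1 gives the lack of data linking PK to pharmacodynamic effect as part of the rationale. A concentration averaged over both conditions cannot be set beside that missed-pill mucus result.

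**Working it through.** **Clock arithmetic.** Put the R-1 pill at t = 0.

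Inputs:

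- Day R sampling times and the R+1 time: table in section 3.8.
- Delayed pill at the R-1 clock time + 6 h, ± 15 min: section 5.1, footnote (j).
- R+1 pill at the R-1 clock time ± 30 min: footnote (k).
- R+1 sample within 30 min before that pill: footnote (x).
- One planned missed dose in the missed-pill period: section 3.6.

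The plan's own labels reproduce:

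- 24 + 3 = 27 h; 24 + 5.5 = 29.5 h; 24 + 6 = 30 h.
- The last Day R sample after the delayed pill: (24 + 7.5) − (24 + 6) = 1.5 h.
- R+1 sample: 48 − 0.5 = 47.5 h after the R-1 pill, in line with the rounded 48 h in section 3.7.1.

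Time since last pill at R+1:

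| Condition | Who | Nominal | With the allowed windows |
|---|---|---|---|
| Delayed | Arm A period 2, Arm B period 3 | 47.5 − 30 = 17.5 h | 47.0 − 30.25 = 16.75 h to 48.5 − 29.75 = 18.75 h |
| Missed | Arm B period 2, Arm A period 3 | 47.5 − 0 = 47.5 h | 47.0 h to 48.5 h |

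The conditions are 30 h apart and their windows do not overlap.

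**Size of the mixing.** The SAP gives no half-life, so this part is an illustration. It assumes one compartment, steady state at R-1, complete absorption before the sample, and k = ln 2 / half-life.

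- Missed: C_m = exp(−47.5k) / (1 − exp(−24k)).
- Delayed: the same residue plus one new dose, C_d = C_m + exp(−17.5k).
- Ratio: C_d / C_m = 1 + exp(30k) − exp(6k).
- Equal-weight pooled mean relative to missed: (ratio + 1) / 2.
- Pooled relative to delayed: (1 + 1/ratio) / 2.

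Worked case, half-life 24 h: exp(30k) = 2^1.25 = 2.378 and exp(6k) = 2^0.25 = 1.189. The ratio is 1 + 2.378 − 1.189 = 2.19, and pooled/missed is 3.19 / 2 = 1.59.

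| Assumed half-life | Delayed / missed | Pooled / missed | Pooled / delayed |
|---|---|---|---|
| 12 h | 5.24 | 3.12 | 0.60 |
| 18 h | 2.91 | 1.96 | 0.67 |
| 24 h | 2.19 | 1.59 | 0.73 |
| 30 h | 1.85 | 1.43 | 0.77 |
| 36 h | 1.66 | 1.33 | 0.80 |

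Over this range the pooled mean overstates the missed-pill value by 212% down to 33%, and understates the delayed-pill value by 40% down to 20%.

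Equal weighting follows from the crossover when both periods are pooled: a woman with both R+1 samples contributes one value to each condition. Within a single period the weights follow the arm sizes.

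**Comparison with a usual pre-dose value.** In the same model, take a regular sample 24 − 0.5 = 23.5 h after a pill. The missed-pill concentration is exp(−24k) times that value: 0.25 at 12 h, 0.50 at 24 h and 0.63 at 36 h. The pooled mean is 0.78, 0.80 and 0.84 times it. A reader of the pooled mean would see a modest dip where the missed-pill concentration has fallen much further.

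**The case against.** The best defence is that the arm labels record who is sampled rather than who is averaged. On Day R, each time point is sampled in only one arm per period, so labelling those entries by arm restates the sampling table and is no evidence of a deliberate split. On this reading, naming both arms at R+1 means only that both give blood. This stands so far as it goes: the contrast with Day R does not prove that pooling was intended. But the list is introduced as the means to be calculated, and the same notation at R-1 is naturally read as pooling.

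A second argument is that the 2/3 notation is shorthand for the two periods respectively, so nothing need be averaged over periods. That may be so, but it does not help, because each period contains both conditions.

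A third is that the SAP elsewhere uses treatment period for the type of period (perfect use, delayed, missed), as in sections 2.2 and 3.7.2.1, so a table for all treatment periods might already separate delayed from missed. Section 3.8 never says so, and its own sampling table is laid out by calendar period and arm.

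The limits on impact do stand. The missed-pill 30 h concentration is reported separately. Listing 16.2.5.3 gives the individual concentrations, so the split can be recovered. The delayed-pill sample at 17.5 h falls after a shortened interval, so it is not a usual trough either. The percentages depend on an assumed half-life and model, and their wide range shows that the documents cannot fix the size.

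**Conclusion.** The concern holds. As written, the R+1 mean combines two conditions whose times since last pill differ by 30 h, and it answers neither part of the PK objective on infringements. This follows from the SAP's own dosing and sampling times and needs no PK model.

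The size does need one. With one-compartment decline, a half-life between 12 and 36 h (assumed) and equal weights, the pooled mean lies about 33% to 210% above the missed-pill mean.

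The effect is confined to a descriptive secondary summary in an exploratory study. No test depends on it, the primary mucus analysis is untouched, and no data are lost. It should be corrected because R+1 is the one value in the three-day period specific to a missed pill.

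**What to change.** In section 3.8, replace the single R+1 entry with two:

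- **Delayed pill:** R+1 concentration from Arm A in period 2 and Arm B in period 3, labelled as 17.5 h after the delayed pill.
- **Missed pill:** R+1 concentration from Arm B in period 2 and Arm A in period 3, labelled as 47.5 h after the last pill.

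State that Table 14.2.21 and Plot 14.2.22 present the delayed/missed pill time points by type of infringement. The R-1 entry can stay pooled.

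The cost is one line of SAP text and a grouping variable in one table and one figure. No further sampling or data collection is needed. If a split was intended all along, the same sentence settles it.

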### 3.4 Analysis Populations

All Enrolled – This population includes all successfully screened subjects enrolled in the study. AE will be primarily used for baseline and demographics tables including disposition.

Safety (SAF) – This population consists of all subjects who took at least one dose of study medication.

The Safety (SAF) set will be used for safety purposes including adverse events, intermenstrual bleedings and labs data, but also to describe the population and to summarize and describe the level of compliance based on daily intake.

Intent-to-Treat (ITT) – This population consists of all subjects who were randomized. ITT will be the primary population used for sensitivity analyses.

The ITT population will be used in the primary sensitivity analysis for assessing the effect of delayed or missed pill on cervical mucus scores and on secondary pharmacodynamic analyses.

Full Analysis Set – This population consists of all **evaluable subjects**. These are subjects who have complete (including mitigated) data on cervical mucus and ovarian activity for the adjudication committee to assess evaluability of a cycle. They will be classified into 3 analysis populations depending on the question of interest. There are 3 full analysis sets defined: Cervical Mucus, Ovarian Activity and Conception Protection. Full analysis set requires at least one evaluable treatment cycle.

- Full Analysis Set – Cervical Mucus (FASM) – This population is composed of all randomized and treated subjects with **cervical mucus** information (mucus score) at the second or third treatment periods for the questions related to mucus on the effect of unperfect use (delayed and missed intake) of norgestrel.
- Full Analysis Set – Ovarian Activity (FASO) – This population consists of all randomized and treated subjects with ovarian activity information (OAS: ovarian activity score) at the second or third treatment periods for questions related to **ovarian activity**.
- Full Analysis Set – Conception Protection (FASC) – This population consists of all randomized and treated subjects with information on mucus and ovarian activity for questions related to **overall conception protection**.

Cycles with a very early ovulation (within 10 days before the DMP period) at period 2 or 3 may be removed from the set of evaluable cycles in a sensitivity analysis or included as failure

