depending upon the question of interest because the effect of intake infringement cannot be assessed in these cycles. The assessment of evaluable cycles, the exclusion of cycles from a given analysis and the exclusion of a subject from the FASM/FASO/FASC will be decided in a blinded manner by an independent adjudication committee.

The FASM, FASO and FASC (or evaluable populations) will be used in the primary analysis for assessing the effect of delayed or missed pill on cervical mucus scores and on secondary pharmacodynamic analyses.

Per-protocol (PP) – This population consists of all subjects from the FASM/FASO/FASC without major protocol violation/deviation and with complete cervical mucus and ovarian activity data for all the three treatment periods. Relevant protocol violation/deviation will be defined during the data review. This will include pill intake compliance issues and early ovulation.

The PP population will be used for assessing the efficacy and PK results without missing data and possibly biased data due to protocol violations/deviations. This will be the "cleanest" results for assessing the effect of infringement and the PD effect at the expense of completeness of the set of randomized women and representativeness of the treated population.

The number of subjects in each population will be summarized for all subjects.

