14.2.20	Summary of Conception Protection	ITT
14.2.21	Summary of PK Concentrations of LNG	Per-Protocol
14.2.22	Plot of PK LNG Concentrations over Time for All Periods	Per-Protocol
14.3.1.1	Incidence of Adverse Events	Safety

Table or Graph Number	Table or Graph Title	Population
14.3.1.2	Incidence of Serious Adverse Events	Safety
14.3.1.3	Incidence of Adverse Events Leading to Discontinuation	Safety
14.3.1.4	Incidence of Adverse Events by Intensity	Safety
14.3.1.5	Incidence of Adverse Events by Relationship to Study Drug	Safety
14.3.1.6	Incidence of Adverse Events Presented in Descending Frequency of Preferred Term	Safety
14.3.2.1	Listing of Subjects with Serious Adverse Events	Safety
14.3.2.2	Listing of Subjects with Adverse Events that Led to Premature Discontinuation	Safety
14.3.5.1	Summary of Treatment Exposure	Safety
14.3.5.2	Summary of Mean Change from Screening to End of Study Visit for Hematology Parameters	Safety
14.3.5.3	Summary of Mean Change from Screening to End of Study Visit for Chemistry Parameters	Safety
14.3.5.4	Summary of Shifts from Screening to End of Study Visit for Hematology Parameters	Safety
14.3.5.5	Summary of Shifts from Screening to End of Study Visit for Chemistry Parameters	Safety
14.3.5.6	Summary of Change from Screening to End of Study Visit for Vital Signs	Safety
14.3.5.7	Number of Days for Subjects with Bleeding and Spotting by Treatment Period	Safety
Listing Number	Listing Title	Population
16.2.1.1	Analysis Populations	All Enrolled
16.2.1.2	Subject Disposition	All Enrolled
16.2.1.3	Inclusion and Exclusion Criteria	All Enrolled
16.2.2	Protocol Deviations	All Enrolled

Listing Number	Listing Title	Population
16.2.3	Patients Excluded from the Analysis Populations	All Enrolled
16.2.4.1	Demographics	All Enrolled
16.2.4.2	Contraceptive History	All Enrolled
16.2.4.3	Gynecological History	All Enrolled
16.2.4.4	Pregnancy History	All Enrolled
16.2.4.5	Substance Use History	All Enrolled
16.2.4.6	Gynecological Assessments	All Enrolled
16.2.4.7	Medical History	All Enrolled
16.2.4.8	Pre-Treatment Signs and Symptoms	All Enrolled
16.2.4.9	Prior and Concomitant Medications	All Enrolled
16.2.5.1	Study Drug Administration	All Enrolled
16.2.5.2	IMP Intake	All Enrolled
16.2.5.3	PK Concentrations of LNG	All Enrolled
16.2.6.1	Cervical Mucus	All Enrolled
16.2.6.2	Transvaginal Ultrasound	All Enrolled
16.2.6.3	Hormones	All Enrolled
16.2.6.4	Ovarian Status	All Enrolled

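### Levonorgestrel concentrations are summarised and plotted only for the per-protocol set, which is selected on later mucus and ovarian data rather than on whether the PK sample is valid

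*SAP*

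**What the plan says.** Section 3.8 summarises levonorgestrel concentrations "for all treatment periods for the PP population". The display list in section 5.5 agrees: table 14.2.21, "Summary of PK Concentrations of LNG", and figure 14.2.22, "Plot of PK LNG Concentrations over Time for All Periods", each carry Per-Protocol as their only population. No PK analysis set is defined in section 3.4.

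Section 3.4 builds the per-protocol set from the full analysis sets, which contain randomised and treated women. It keeps those without a major deviation and "with complete cervical mucus and ovarian activity data for all the three treatment periods". On the deviations that count, it adds: "This will include pill intake compliance issues and early ovulation".

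The assignment is intended. Section 3.4 states: "The PP population will be used for assessing the efficacy and PK results without missing data". It also accepts that the set is obtained "at the expense of completeness of the set of randomized women and representativeness of the treated population".

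**The concern.** Two of the per-protocol criteria have nothing to do with whether a plasma concentration can be interpreted. Completeness of mucus and ovarian data is a property of other measurements. Early ovulation is a pharmacodynamic result. Only pill-intake compliance bears on the PK sample, and no criterion named in the definition concerns PK sampling time or assay validity.

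The secondary objectives in section 2.2 include the kinetics after a single dose and at steady state. Samples for both are taken in period 1, yet whether they are summarised depends on events in periods 2 and 3. Section 2.1 motivates the study by the lack of data connecting PK with pharmacodynamic action in progestin-only pills. Choosing the PK sample by a pharmacodynamic outcome works against that purpose, because the concentrations of women who ovulate early are among those a reader would most want to see summarised.

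At stake are the precision of the mean concentrations and, if exclusion is related to exposure, their accuracy.

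**Working it through.** The SAP states no figure for this point, so there is none to reproduce. The check is one of text and timing, followed by simple arithmetic.

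**1. When samples are taken and when exclusion is decided**

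| Item | Timing | Source |
|---|---|---|
| Single-dose samples | Day 1 | 3.8 |
| Steady-state samples | First visit of week 3, in period 1 | 3.8; 5.1 note (s) |
| Randomisation, needed for per-protocol | First visit of period 2 | 5.1 note (d) |
| Early ovulation | "Cycles with a very early ovulation (within 10 days before the DMP period) at period 2 or 3" | 3.4 |
| Complete mucus and ovarian data | All three periods | 3.4 |

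The per-protocol paragraph does not define early ovulation. I read it with the definition given just before it in section 3.4. A valid Day 1 or week 3 concentration then leaves the summaries if the woman stops before randomisation, ovulates early in period 2 or 3, or has incomplete mucus or ovarian data in any period.

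**2. Scheduled samples affected per woman** (3.8)

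- Day 1: 4 (odd and even subject numbers each have four times)
- Week 3: 1 (afternoon visit) or 2 (morning visit)
- Weeks 5 and 9: 1 each, so 2 (taken for compliance, 5.1 note (t))
- Delayed/missed-pill windows: 5 in the delayed-pill period and 3 in the missed-pill period, so 8

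Total: 4 + (1 to 2) + 2 + 8 = 15 to 16. This is the count for a fully sampled woman; one who leaves early contributes fewer.

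**3. Precision**

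Inputs: 45 completers (2.5); odd/even split on Day 1 (3.8); per-protocol fraction f, assumed 0.7 to 0.9. If exclusion is unrelated to concentration, the width of an interval for a mean scales as 1/√f.

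| f | Women, 45 × f | Per Day 1 time point, 45 × f / 2 | Width ratio, 1/√f |
|---|---|---|---|
| 1.0 | 45 | 22.5 | 1.00 |
| 0.9 | 40.5 | 20.2 | 1.05 |
| 0.8 | 36 | 18.0 | 1.12 |
| 0.7 | 31.5 | 15.7 | 1.20 |

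Day 1 sampling covers all subjects, not only completers. If 45 do complete, 22.5 per time point is a minimum for a set that does not depend on later events.

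**4. Possible bias, illustration only**

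Take a lognormal concentration with between-subject CV 30% or 50%. Let the log-odds of exclusion fall linearly in log-concentration, with odds ratio OR per SD lower. The bias is the retention-weighted mean divided by the full mean, minus 1. None of these inputs is in the SAP.

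- OR = 1: about 0%.
- OR 1.5, CV 30%, 10% excluded: +1.0%.
- OR 2, CV 30% or 50%, 20% excluded: +3.5% or +5.6%.
- OR 3, CV 50%, 30% excluded: +11.7%.

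The positive sign follows from assuming that lower exposure makes exclusion more likely; the opposite association would reverse it. The model also ties every exclusion to concentration, so the upper end is generous.

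**The case against.** The strongest defence is that the choice is deliberate, consistent across sections 3.4, 3.8 and 5.5, and made with its cost stated. The compliance criterion is sensible for PK, since a concentration after undocumented dosing is hard to interpret. The study is exploratory, PK is a secondary objective summarised descriptively without a test, and it does not enter the primary mixed model. All of this stands. It limits the importance of the point and shows that there is no internal contradiction. It does not explain why mucus completeness or early ovulation should decide which concentrations are averaged. The main mucus, ovarian and conception-protection displays are each planned on a full analysis set, per-protocol and ITT, whereas PK has no second set against which to see the effect of selection.

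Three stronger readings are tempting but not supported:

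- *Valid samples are thrown away.* Listing 16.2.5.3 covers All Enrolled, so they are reported individually. They are missing only from the summary and the plot.
- *One missed mucus or ultrasound assessment removes a woman.* Section 3.4 gives no visit-level rule for completeness. The parent full analysis set accepts mitigated data, an adjudication committee judges evaluability, and section 3.7.2.1 needs only seven mucus assessments per period for its own summaries.
- *Mean concentrations will be too high.* This requires women with low exposure to be the ones removed. The SAP gives no evidence linking concentration to early ovulation or to incomplete data, and section 2.1 says such PK-to-pharmacodynamic data are lacking.

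**Conclusion.** The point holds as a weakness in the choice of population. Both planned PK displays rest on a set selected partly by pharmacodynamic outcome and data completeness, so period 1 concentrations can be left out for reasons that arise after they were measured and that say nothing about their validity.

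The loss of precision is modest: about 5-20% wider intervals if 10-30% of women are not per-protocol. It is felt most on Day 1, where each time point already uses only about half the women. Bias is possible, but its direction and size cannot be determined from the SAP; it is about zero if exclusion is unrelated to exposure. The 10-30% rate and all inputs to the bias illustration are assumptions. The primary analysis is unaffected. The change is worth making because it is cheap and because the study exists partly to relate PK to pharmacodynamics.

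**What to change.** In section 3.4, define a PK set: all treated women with at least one valid measured levonorgestrel concentration and documented dosing and sampling times. Values below the quantification limit should count as measured. Requiring a quantifiable level would itself select on exposure.

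In section 3.8, make this the main population and exclude an individual sample only for a dosing or timing deviation that affects that sample. State how values below the quantification limit enter the summary statistics.

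In section 5.5, assign the PK set to 14.2.21 and 14.2.22 and add per-protocol versions as supportive displays.

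Cost: one extra population flag, one extra set of displays and the wording. No new data are needed.
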